6.2 Secondary endpoints

6.2.1 Immunogenicity endpoints – Part A

6.2.1.1 GMT and GMFR of Reference and VOC specific NT at each specified post-vaccination time point

The number of subjects with valid and determinate assay results for the specified assay at each given dose/sampling time point, GMT, GMFRs, and the associated 2-sided 95% CIs will be provided by Cohort based on Immunogenicity Analysis Set. GMFR will be presented from before vaccination to each specified post-vaccination time point.

Also, bar charts including LLOQ and ULOQ lines and with different color codes for data from subjects according to their N-binding assessment for the respective visit, time point and line plots with mean and 95% CIs over time by Cohort and trial part will be presented for VOC and the reference strains.

The analysis described above will also be performed on Immunogenicity Analysis Per Protocol Set.

6.2.1.2 SR to reference and VOC specific NT at each specified post-vaccination time point

The number and percentage of subjects with SR, including the associated 2-sided 95% CI at each specified post-vaccination time point will be provided by Cohort based on Immunogenicity Analysis Set.

The above analyses will also be performed on immunogenicity per protocol set.

6.2.2 Immunogenicity endpoints – Part B

6.2.2.1 GMT of Reference and VOC specific NT at 1 month after one dose of BNT162b2 (B.1.1.7 + B.1.617.2) and Dose 2 of BNT162b2

The same analysis as described in [Section 6.2.1.1](#) will be repeated for Part B Cohorts 1 at 1 month after one dose of BNT162b2 (B.1.1.7 + B.1.617.2) and Dose 2 of BNT162b2 for subjects from the Phase III trial BNT162-02 / C4591001.

6.2.2.2 SR of Reference and VOC specific NT at 1 month after one dose of BNT162b2 (B.1.1.7 + B.1.617.2) and Dose 2 of BNT162b2

The same analysis as described in [Section 6.2.1.2](#) will be repeated for Part B Cohorts 1 at 1 month after one dose of BNT162b2 (B.1.1.7 + B.1.617.2) and Dose 2 of BNT162b2 for subjects from the Phase III trial BNT162-02 / C4591001.

6.2.2.3 GMT of Reference and VOC specific NT at 1 month after one dose of BNT162b2 (B.1.617.2) and Dose 2 of BNT162b2

The same analysis as described in [Section 6.2.1.1](#) will be repeated for Part B Cohorts 4 at 1 month after one dose of BNT162b2 (B.1.617.2) and Dose 2 of BNT162b2 for subjects from the Phase III trial BNT162-02 / C4591001.

6.2.2.4 SR of Reference and VOC specific NT at 1 month after one dose of BNT162b2 (B.1.617.2) and Dose 2 of BNT162b2

The same analysis as described in [Section 6.2.1.2](#) will be repeated for Part B Cohorts 4 at 1 month after one dose of BNT162b2 (B.1.617.2) and Dose 2 of BNT162b2 for subjects from the Phase III trial BNT162-02 / C4591001.

6.2.2.5 GMT of Reference and VOC specific NT at 1 month after Dose 2 and Dose 3 of BNT162b2 (B.1.1.7 + B.1.617.2) for Cohort 6 in COVID-19 vaccine-naïve subjects

The same analysis as described in [Section 6.2.1.1](#) will be repeated for Part B Cohorts 6 at 1 month after Dose 2 and Dose 3.

6.2.2.6 SR of Reference and VOC specific NT at 1 month after Dose 2 and Dose 3 of BNT162b2 (B.1.1.7 + B.1.617.2) for Cohort 6 in COVID-19 vaccine-naïve subjects

The same analysis as described in [Section 6.2.1.2](#) will be repeated for Part B Cohort 6 at 1 month after Dose 2 and Dose 3.

6.2.2.7 GMTs and GMRs of VOC specific NTs at 3 weeks after 1 dose BNT162b2 (B.1.1.7 + B.1.617.2) in COVID-19 vaccine-naïve subjects vs VOC specific NTs at 1 month after one booster dose of BNT162b2 (B.1.1.7 + B.1.617.2) in BNT162b2-experienced subjects (Cohort 6 with prior infection vs Cohort 1 without prior infection)

The same analysis as described in [Section 6.1.2.5](#) will be repeated for Part B Cohort 6 vs Cohort 1 comparison.

6.2.2.8 SRs and differences in SRs of VOC specific NT at 3 weeks after 1 dose of BNT162b2 (B.1.1.7 + B.1.617.2) in COVID-19 vaccine-naïve subjects vs VOC specific NTs at 1 month after one booster dose of BNT162b2 (B.1.1.7 + B.1.617.2) in BNT162b2-experienced subjects (Cohort 6 with prior infection vs Cohort 1 without prior infection)

The same analysis as described in [Section 6.1.2.6](#) will be repeated for Part B Cohort 6 at vs Cohort 1 comparison.

6.2.2.9 GMTs and GMRs of VOC specific NTs at 3 weeks after 1 dose of BNT162b2 (B.1.1.7 + B.1.617.2) in COVID-19 vaccine-naïve subjects with prior infection vs VOC specific NTs at 1 month after 2 doses of BNT162b2 (B.1.1.7 + B.1.617.2) in COVID-19 vaccine-naïve subjects without prior infection (Cohort 6 with prior infection vs Cohort 6 without prior infection)

The same analysis as described in [Section 6.1.2.5](#) will be repeated for Part B Cohort 6 with prior infection vs Cohort 6 without prior infection.

6.2.2.10 SRs and differences in SRs of VOC specific NT at 3 weeks after 1 dose of BNT162b2 (B.1.1.7 + B1.617.2) in COVID-19 vaccine-naïve subjects with prior infection vs VOC specific NTs at 1 month after 2 doses of BNT162b2 (B.1.1.7 + B1.617.2) in COVID-19 vaccine-naïve subjects without prior infection (Cohort 6 with prior infection vs Cohort 6 without prior infection)

The same analysis as described in [Section 6.1.2.6](#) will be repeated for Part B Cohort 6 with prior infection vs Cohort 6 without prior infection.

6.2.3 Immunogenicity endpoints – Part C

6.2.3.1 GMT of VOC specific NT at baseline and at each post-vaccination time point for Cohorts 7, 8 and 9

The same analysis as described in [Section 6.2.1.1](#) will be repeated for Part C Cohorts 7, 8 and 9.

A bar chart including LLOQ and ULOQ lines and with different color codes for data from subjects according to their N-binding assessment for the respective visit, time point and line plot of GMTs and the associated 2-sided 95% CIs will be presented at each post-vaccination time point for each cohort by trial part.

The analysis will be performed on Immunogenicity Analysis Per Protocol Set as well. The number of subjects with valid and determinate assay results for the specified assay at each post-vaccination time point and a summary of GMT and its associated 2-sided 95% CIs will be presented by cohort.

6.3 Exploratory endpoints

6.3.1 Exploratory – Part A

The exploratory analyses not specified in [Section 6.3](#) are out of scope of this SAP and may be described in a different document.

6.3.1.1 CD4+ and CD8+ T-cell responses (Ex vivo ELISpot)

Only descriptive analyses will be performed and no formal hypotheses will be tested for these exploratory endpoints.

In the clinical trial report, only fitness-normalized T-cell response data (normalized background is subtracted from the normalized experiment spot count to account for varying background when comparing samples) will be analyzed and all spot counts are extrapolated to number of spots per 10⁶ cells.

All analyses on Ex vivo ELISpot data will be performed on the Immunogenicity Analysis Set. If applicable, analyses may be performed on the Immunogenicity Analysis Per Protocol Set as well.

Visits for blood draws for T-cell responses with visit windows can be found in [Table 7](#). Window per CTP and additional grace period will be applied for the respective analysis set in the table.

Imputation and missing values:

Missing values for Ex vivo ELISpot data will not be imputed. Ex vivo ELISpot data outside the respective sampling windows applicable for the analysis in [Table 7](#) will not be included in the analyses. No limit of detection applies to this endpoint.

If expert call responses for the combined target “spike protein pools 1 + 2” are not derived in the source data, they will be derived as follows:

- positive response: if at least one of spike protein pool 1 and spike protein pool 2 has a positive response
- no response: if both spike protein pool 1 and spike protein pool 2 have no response
- not evaluable: otherwise (if both spike protein pool 1 and spike protein pool 2 are not evaluable, if one of the spike protein pools has no response and the other is not evaluable).

Analysis:

ELISpot results per sample and subject response evaluation results will be reported separately for each T-cell type (CD4+ T-cells, CD8+ T-cells) and for each variant.

Spot counts will be summarized with Mean, SD, Median, Q1, Q3, Min and Max by cohort (in part A: Cohorts 1-6 separately), variant (FL-S, FLS B.1.1.7, FLS B.1.617.2), target (spike protein pool 1, spike protein pool 2, sum of spike protein pool 1 + 2), and sampling time point (visit relative to dose: Day 1, Day 8, Day 29, Day 180, Day 360) if there is data available. Moreover, responses (expert calls: positive response, no response, not evaluable) will be summarized in the same manner for all applicable sampling time points.

Scatterplots for IFNg spot assessments over time will be produced comparing cohorts per variant and target. Moreover, boxplots (with min, max, median, quartiles) for Day 8 and Day 29 will be produced comparing cohorts per variant and target.

Spot count and expert call response data used in the analysis will be listed per subject for all assessments in the Immunogenicity Analysis Set.

All tables, figures and listings for this endpoint will be produced separately for CD4+- and for CD8+- T-cells.

6.3.2 Exploratory – Part B

6.3.2.1 GMT, GMFR and SR of Reference and VOC specific NT at each post vaccination time point for Cohort 1 and 4 in BNT162b2-experienced subjects

The same analysis as described in [Section 6.2.1.1](#) will be repeated for GMT and GMFR at each post-vaccination time point.

The same analysis as described in [Section 6.2.1.2](#) will be repeated for SR at each post-vaccination time point.

6.3.2.2 GMT, GMFR and SRs of Reference and VOC specific NT at each post vaccination time point for Cohort 6 in COVID-19 vaccine-naïve subjects

The same analysis as described in [Section 6.2.1.1](#) will be repeated for GMT and GMFR at each post-vaccination time point.

The same analysis as described in [Section 6.2.1.2](#) will be repeated for SR at each post-vaccination time point.

6.3.2.3 Number of confirmed COVID-19 cases

The number and percentage of subjects reporting a confirmed COVID-19 case during the surveillance period will be presented by Cohort. In addition, the incidence of confirmed COVID-19 cases per 1,000 person-years of follow-up will also be presented.

6.3.2.4 Nucleocapsid-binding antibody seroconversion

The same analysis as described in [Section 6.3.2.3](#) will be repeated for the incidence of N-binding antibody seroconversion.

6.3.3 Exploratory – Part C

6.3.3.1 GMT, GMFR and SR of Reference and VOC specific NT at baseline and post-vaccination time point for Cohorts 7, 8 and 9

The same analysis as described in [Section 6.2.1.1](#) will be repeated for GMT and GMFR at baseline and post-vaccination time point for Cohort 7, 8 and 9.

The same analysis as described in [Section 6.2.1.2](#) will be repeated for SR at baseline and post-vaccination time point for Cohort 7, 8 and 9.

6.3.3.2 Number of confirmed COVID-19 cases

The same analysis as described in [Section 6.3.2.3](#) will be conducted for all Part C Cohorts.

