## Part C

Part C consists of n = ~225 subjects who previously received two or three injections of any authorized COVID-19 RNA-based vaccine and were subsequently diagnosed with SARS-CoV-2 infection from January 2022 onwards (limited to a period when there was a high prevalence of SARS-CoV-2 Omicron infections).

Subjects in Part C will be randomized in a 2:2:1 ratio into three cohorts; ~90 subjects each in Cohorts 7 and 8 (to ensure ~80 evaluable subjects in each cohort after 11% dropout) and 45 subjects in Cohort 9. Randomization will be stratified by age group (18 to 55 years of age or 56 to 85 years of age) and by number of prior doses of COVID-19 RNA-based vaccine (two or three doses).

The sponsor may terminate the enrollment into Cohort 9 at any time in case the evolving COVID-19 epidemiology and/or the recommendations issued in the context of national vaccination campaigns no longer support enrollment of the trial population in a realistically feasible time.

Cohorts 7 to 9 will enroll subjects 18 to 85 years old; ~60% of these subjects should be 18 to 55 years old and ~40% should be 56 to 85 years old:

- **Cohort 7:** Subjects will receive one dose of 30 µg monovalent vaccine BNT162b2 (B.1.1.529) on Day 1.
- **Cohort 8:** Subjects will receive one dose of 30 µg BNT162b2 on Day 1.
- **Cohort 9:** No vaccination will be given to Cohort 9 subjects within 3 months after Visit 1. After the 3-month follow-up period, subjects in Cohort 9 will be offered a BNT162b2 vaccination, depending on the epidemiological situation, local regulatory authority recommendations, and/or variant vaccine authorization status.

Approximately 25 subjects at preselected sites in each cohort of Part C will be evaluated in terms of cell-mediated immunity.

For a summary of the trial as a flow diagram, see the Schema in Section 1.2. For the planned assessments and visits, see the SoA in Section 1.3.

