- Part C of the trial will characterize the safety of BNT162b2 and BNT162b2 (B.1.1.529) in subjects who are COVID-19 RNA-based vaccine-experienced and have subsequently experienced a SARS-CoV-2 infection.

- Part C further allows assessment of the immune responses to each antigen (i.e., the S protein of the reference ancestral SARS-CoV-2 strain [Wuhan-Hu-1/USA-WA1] or B.1.529). Part C also allows assessment of whether vaccination with the Omicron-specific vaccine BNT162b2 (B.1.1.529) in COVID-19 RNA-based vaccine-experienced individuals who experienced a SARS-CoV-2 Omicron breakthrough infection:
  - Is quantitatively superior to the immune response after one dose of the parental vaccine BNT162b2.
  - Elicits a qualitatively improved anamnestic response able to cross-neutralize conserved and unique strain epitopes.
- The thorough clinical comparison of the variant-specific vaccine BNT162b2 (B.1.529) with the parental vaccine BNT162b2 in COVID-19 RNA-based vaccine-experienced individuals that had a breakthrough infection in Part C will generate information on the comparative breadth and magnitude of immune responses in this situation, potentially supporting the choice of booster vaccine in this population.
- The subjects who will not receive a BNT162b2-based vaccine in Cohort 9 in Part C will bring valuable information about the magnitude, quality, and duration of immune responses post breakthrough infection in COVID-19 RNA-based vaccine-experienced individuals that will serve to contrast responses after an additional vaccination with the variant-specific vaccine BNT162b2 (B.1.529) or with the parental vaccine BNT162b2.

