### 9.2.3 Part C

No confirmatory hypothesis testing is planned for Part C. However, exploratory analysis may be performed on selected endpoints. To describe the immune profile 80 evaluable subjects per cohort in Cohorts 7 and 8 and 40 evaluable subjects in Cohort 9 are considered adequate based on experience in previous trials conducted by BioNTech in the BNT162 program.

Table 13 below demonstrates the power for testing GMT for variant strain post BNT162b2 vs post BNT162b2 (B.1.1.529) at alpha = 0.025 (1-sided) to demonstrate superiority.

To account for ~11% non-evaluable rate, Part C will randomize 225 subjects in a 2:2:1 ratio (90 each for Cohorts 7 and 8 and 45 in Cohort 9).

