**Table 13: Power analysis for immunogenicity GMT comparison**

Test	Margin	Assumed GMR (GMT variant ÷ GMT ref)	Number of evaluable subjects	Standard deviation (log value)	Power
GMT superiority	1.0	1.75	80	1.0	94%

Margin is the lower bound of 95% CI for GMR.

GMT = geometric mean titer; GMR = geometric mean ratio.

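### The Part C COVID-19 case table puts undosed Cohort 9 (end of trial at Day 85) beside Cohorts 7 and 8 (Day 360) with no common window and no surveillance start for Cohort 9

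*SAP*

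**What the plan says.** - **Cohorts in the analysis.** SAP 6.3.3.2 states that the case analysis of SAP 6.3.2.3 "will be conducted for all Part C Cohorts".
- **What is tabulated.** SAP 6.3.2.3 gives, by cohort, the number and percentage of subjects with a confirmed case during the surveillance period. It adds that "the incidence of confirmed COVID-19 cases per 1,000 person-years of follow-up will also be presented".
- **The clock.** In SAP 3.3.1, surveillance begins after the first vaccination and ends at the first confirmed case or the subject's end of trial. SAP 3.1.1 says Cohort 9 is not dosed.
- **Length of follow-up.** In Protocol 1.3, end of trial is Day 360±10 for Cohorts 7 and 8 (Table 6) and Day 85±5 for Cohort 9 (Table 7).
- **The objective.** Protocol Section 3 (Part C, exploratory) and SAP Table 4 limit the incidence objective to subjects who received one dose of either vaccine, over a one-year period.
- **Enrolment.** Protocol 4.1 states: "The sponsor may terminate the enrollment into Cohort 9 at any time in case the evolving COVID-19 epidemiology".

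SAP Section 2 says that departures from the protocol analysis are documented in SAP Section 8. The inclusion of Cohort 9 in the case analysis is not listed there.

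**The concern.** Three randomised cohorts will appear side by side in one case table, and a reader will naturally compare the unvaccinated column with the two vaccinated ones. Those columns cover different stretches of time.

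The percentage makes no allowance for length of follow-up. The person-year rate does, but it averages the hazard over about 3 months in one cohort and about 12 in the others. The averages match under no vaccine effect only if the hazard is flat. The protocol's own rationale describes infection incidence peaking in January 2022, so a flat hazard cannot be taken for granted. Time since vaccination changes over the same months.

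Because Cohort 9 has no dose, its surveillance start also cannot be derived from the SAP as written. The programmer would have to choose one.

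**Working it through.** **Inputs from the documents.** Part C sizes are in Protocol 9.2.3: "To account for ~11% non-evaluable rate, Part C will randomize 225 subjects in a 2:2:1 ratio", that is 90, 90 and 45. End-of-trial days are 360 and 85 (Protocol 1.3, Tables 6 and 7). One year is 365.25 days (SAP 3.4.2).

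**The plan's own figures.** 80/(1 − 0.11) = 89.9, rounded up to 90. 40/(1 − 0.11) = 44.9, rounded up to 45. The total is 90 + 90 + 45 = 225, as stated. The 94% power in Protocol Table 13 also reproduces: ln(1.75) × √(80/2)/1.0 = 3.54, and Φ(3.54 − 1.96) = 94.3%. That power concerns Cohort 7 versus Cohort 8 and does not bear on this point.

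**Follow-up per subject.** Cohort 9: 85/365.25 = 0.233 years. Cohorts 7 and 8: 360/365.25 = 0.986 years. The ratio is 360/85 = 4.24.

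**Assumption.** The documents give no COVID-19 hazard, so the hazards below are assumed and shown over a range. The vaccine effect is set to none throughout.

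**Percentage with a case, constant hazard h:** 1 − exp(−h × time).

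| h per year | Cohort 9 (85 days) | Cohorts 7, 8 (360 days) | Ratio |
|---|---|---|---|
| 0.1 | 2.3% | 9.4% | 4.1 |
| 0.3 | 6.7% | 25.6% | 3.8 |
| 0.5 | 11.0% | 38.9% | 3.5 |
| 1.0 | 20.8% | 62.7% | 3.0 |

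**Person-year rate, hazard h1 to Day 85 and h2 afterwards, first case only.** Let t1 = 0.233 and t2 = 275/365.25 = 0.753. In Cohorts 7 and 8:

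- expected cases per subject = 1 − exp(−h1·t1 − h2·t2);
- expected person-years per subject = [1 − exp(−h1·t1)]/h1 + exp(−h1·t1) × [1 − exp(−h2·t2)]/h2.

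The Cohort 9 rate is h1. For h1 = 0.3 and h2 = 0.15, cases are 0.167 and person-years 0.889. The rate is 0.188, and 0.188/0.3 = 0.63.

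| h2/h1 (h1 = 0.3) | Rate ratio, Cohorts 7, 8 to Cohort 9 |
|---|---|
| 0.25 | 0.44 |
| 0.5 | 0.63 |
| 1 | 1.00 |
| 2 | 1.72 |
| 4 | 3.02 |

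**With a common 85-day window** both ratios are 1.0 under no vaccine effect, whatever shape the hazard takes, provided the cohorts were enrolled concurrently.

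**Person-time at planned size** (ignoring dropout and censoring at the first case). Cohort 7 or 8: 90 × 0.986 = 88.7 PY to Day 360, and 90 × 0.233 = 20.9 PY to Day 85. Cohort 9: 45 × 0.233 = 10.5 PY. At 0.3 per year, Cohort 9 would yield about 45 × 6.7% = 3 cases.

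**The case against.** **This is an exploratory table with no planned comparison.** The SAP specifies no ratio, difference or test against Cohort 9. Part C has no confirmatory testing (SAP 5.1.4.3), and its GMR and seroresponse-difference analyses compare Cohort 7 with Cohort 8 only (SAP 6.1.3). This stands, and it caps the importance of the point.

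**Person-years already adjust for follow-up, and Cohort 9 is tiny.** With about 10.5 PY the Cohort 9 rate will be very imprecise, and the distortion could sit within its confidence interval. This is fair for the rate. It does not help the percentage, which is distorted even at a constant hazard, nor does it supply the missing start date.

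**Tempting stronger readings.** A reader might infer three further things that the documents do not support.

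- *That the titer results are distorted in the same way.* The secondary estimand gives Cohort 9 GMTs at baseline, 7 days, 1 month and 3 months, and reserves 6 and 12 months for Cohorts 7 and 8. SAP 6.2.3.1 reports by time point, so unequal follow-up adds no bias at a matched visit.
- *That the randomised contrast is confounded by calendar time.* Protocol 4.1 says: "Subjects in Part C will be randomized in a 2:2:1 ratio into three cohorts", stratified by age group and number of prior doses. Enrolment falls out of step only if Cohort 9 closed early while Cohorts 7 and 8 continued. That is permitted, but nothing shows it happened. If it did, titers could also be affected. For example, assume closure at 50% of accrual and later enrollees' GMT at 0.67 to 1.5 times the earlier level. The all-subject GMR against Cohort 9 would then shift by √0.67 = 0.82 to √1.5 = 1.22. SAP 6.5.1.1 tabulates time since infection and time since last vaccination by cohort, so some of this drift would be visible.
- *That Cohort 9 exists to estimate vaccine protection.* Protocol 4.2 describes information on immune responses "that will serve to contrast responses after an additional vaccination with the variant-specific vaccine". It does not mention COVID-19 rates.

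**Conclusion.** The point holds for the case table. As written, SAP 6.3.3.2 goes beyond the protocol objective without recording the change, has no start of surveillance for an undosed cohort, and tabulates figures over 85 and 360 days as if they were comparable.

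Under no vaccine effect, the percentage would be about 3.0 to 4.1 times higher in Cohorts 7 and 8 for constant hazards of 1.0 down to 0.1 per year. The rate ratio would be about 0.63 or 1.72 if the hazard starts at 0.3 per year and halves or doubles after Day 85, and 1.0 only if it is constant. All these sizes rest on assumed hazards. What rests on the documents alone is the 4.24-fold difference in follow-up and the undefined start.

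The reach is limited to an exploratory, descriptive output. No primary result or decision rule changes. The documents do not establish confounding by calendar time; that would require an actual early closure of Cohort 9 with the other cohorts still enrolling.

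**What to change.** 1. **SAP 3.3.1:** start Cohort 9 surveillance at Visit 1. SAP 3.1.1.3 already uses Visit 1 as the starting point for Cohort 9 adverse events.
2. **SAP 6.3.3.2:** report number, percentage and incidence for Cohorts 7, 8 and 9 from Day 1 (Visit 1) to the 3-month (Day 85) visit.
3. **SAP 6.3.3.2:** report 12-month incidence for Cohorts 7 and 8 only, as the protocol objective states.
4. **SAP Section 8:** record that the Cohort 9 case summary is an addition to the protocol.
5. **Conditional:** only if Cohort 9 enrolment was in fact closed early while Cohorts 7 and 8 continued, restrict side-by-side summaries with Cohort 9 (cases and GMT) to subjects randomised while Cohort 9 was open. SAP 8.3 gives the global end of trial as 04 October 2023 and the current SAP is dated February 2024, so this is a matter of record.

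**Cost.** SAP wording and one extra table, with no new data. The common window holds fewer events: about 21 PY instead of about 89 in each of Cohorts 7 and 8, against about 10.5 in Cohort 9. Estimates for that window will be imprecise and should be presented as descriptive.
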